### **2.2 Secondary Objectives**

- 2.2.1 To describe the pharmacokinetics of PTC299 in patients with HIV-associated KS.
- 2.2.2 To describe the effects of PTC299 on serum and plasma VEGF, VEGFR and cytokine profiles in patients with HIV-associated KS.
- 2.2.3 To describe the effects of PTC299 on HIV and KSHV viral loads.
- 2.2.4 To describe the effects of PTC299 on T-lymphocyte subsets (CD4 and CD8).
- 2.2.5 To describe the effects of PTC299 on KS tumor biopsies with respect to expression of VEGF, the VEGFR-2 and -3, phospho-Akt, p53, HIF-1 $\alpha$  and proliferation, measured by Ki-67 staining.
- 2.2.6 To describe the effects of PTC299 on viral gene expression and cellular gene transcription in KS tumor biopsies using real-time QPCR-based profiling.

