## 4.2 Evaluations During Treatment

Evaluations may occur up to 3 days before or after the end of the study visit indicated, unless otherwise noted. Each cycle will be 28 days. Evaluations will continue as outlined below.

- 4.2.1 Clinical assessment at Days 15 ( $\pm$  2) of cycle 1, and then Day 1 on cycle 2 and every cycle thereafter to include an assessment of the following at every visit unless otherwise specified:
- 4.2.1.1 KS tumor assessment Day 1 of cycle 2 and every cycle thereafter. Response of KS to treatment will be assessed as described in Section 8.0. Photographic documentation of lesions will be completed at each visit when the KS response category changes. For example, if a participant's KS response category changes from no response (stable disease) to partial response, the site will take photos of this to document the category change. If there was no change in the KS response category, no photos are required. Refer to Appendix XIV for lesion photography guidelines.
  - 4.2.1.2 A complete physical exam including: vital signs, weight, Karnofsky performance status (Appendix II) and toxicity evaluation.
  - 4.2.1.3 Signs and symptoms review.
  - 4.2.1.4 Complete blood count with differential and platelets.
  - 4.2.1.5 INR and aPTT.
  - 4.2.1.6 Serum chemistries: liver enzymes (AST, ALT, alkaline phosphatase), BUN, creatinine, electrolytes (sodium, potassium, chloride, bicarbonate), calcium, phosphorus, glucose, total protein, albumin, bilirubin (direct and indirect), triglycerides and total cholesterol. If the triglycerides and/or total cholesterol increases to  $\geq$  grade 3, then these values should be rechecked in a fasting state and the cholesterol fractionated.
  - 4.2.1.7 Urinalysis
  - 4.2.1.8 For women of childbearing potential: serum  $\beta$ -HCG at any time pregnancy is suspected.
  - 4.2.1.9 All HIV-related and AIDS-defining events (Appendix XII) and concomitant prescription and over the counter medications, vitamins and supplements taken since the last visit.
  - 4.2.1.10 CD4 count on Day 29 (Day 1 of cycle 2) and every three cycles (12 weeks) thereafter.
  - 4.2.1.11 Plasma HIV-1 RNA on Day 29 (Day 1 of cycle 2) and every three cycles (12 weeks) thereafter.
  - 4.2.1.12 KSHV viral load on Day 29 (Day 1 of cycle 2) and every three cycles (12 weeks) thereafter.

4.2.1.13 Blood for ACTH and cortisol on Day 29 (Day 1 of cycle 2) and every cycle thereafter.

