### 4.3 Evaluations at the Time of Treatment Discontinuation

At the time of treatment discontinuation all evaluations should be completed as soon as possible (see Appendix I, Schedule of Evaluations). The following should be performed upon discontinuation of study drug:

4.3.1 Complete blood count with differential and platelets.

4.3.2 Serum chemistries: liver enzymes (AST, ALT, alkaline phosphatase), BUN, creatinine, electrolytes (sodium, potassium, chloride, bicarbonate), calcium, phosphorus, glucose, total protein, albumin, bilirubin (direct and indirect), triglycerides and total cholesterol.

4.3.3 CD4 count and HIV plasma RNA viral load, and KSHV viral load.

4.3.4 Complete physical examination including: vitals signs, weight, Karnofsky performance status (Appendix II) and toxicity evaluation.

4.3.5 Blood for ACTH and cortisol.

4.3.6 KS tumor assessment. Response of KS to treatment will be assessed as described in Section 8.0. Marker lesions and other areas will be photographed (Appendix XIV).

4.3.7 Cytokine assay (Appendix IV).

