#### **4.4 Post-treatment Evaluation and Evaluation at Early Discontinuation of Therapy**

Thirty days after discontinuation of therapy, a follow-up visit will include the following procedures: complete physical examination (including vitals signs, weight, and tumor assessment, and lesion photography if the response category changed), Karnofsky performance status (Appendix II), toxicity evaluation and cytokine assay.

At a subject's final study visit, the Off-Study Form will be completed and permanent discontinuation of drug will be documented.

Subjects who withdraw for toxicity reasons should be followed until the toxicity resolves/returns to baseline, or for at least 1 month, whichever is later. In addition, subjects who go off study for reasons other than toxicity should be followed for at least 1 month after discontinuing drug.

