In Stage 3, a minimum of 12 patients will be treated at the maximally treated dose. If the underlying response rate is no greater than 10%, then the probability of observing 4 or more responses among 12 patients will be  $< 5\%$ . Thus, if there are 4 or more responses among 12 patients, it can be inferred that the response rate is  $> 10\%$ .

The minimum number of subjects to be entered in the study is **three** (i.e., if  $\geq$  two subjects experience DLT at the lowest dose level in Stage 1).

The maximum number of evaluable subjects to be enrolled in the study is **38** (i.e., 9 subjects have been enrolled into Stage 1, 8 subjects have been enrolled into Stage 2, and up to 21 subjects will be enrolled to Stage 3). Assuming that  $\sim 15\%$  of subjects will not be evaluable for response, we estimate that the maximum number of subjects in the study will be **44**.

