Immunohistochemistry (IHC) will be used to determine expression of the following: VEGF, VEGFR-2, VEGFR-3, phospho-Akt, KSHV LANA, orf59, p53 and HIF-1 $\alpha$ . We will count the number of positive cells per HPF for a total of 10 fields per section and derive an index value. We will consider a 50% change from baseline in the index value for the aforementioned markers a biological response. For each measure (VEGF, VEGFR-2, VEGFR-3, phospho-Akt, KSHV LANA, orf59, p53 and HIF-1 $\alpha$ ), we will estimate the proportion of patients who demonstrate a 50% change between baseline and on treatment (between day 22 and day 28) value. The exact binomial 95% confidence interval will be derived for each measure.

To evaluate the effects of PTC299 on tumor cell proliferation, the change in immunohistochemistry of Ki67 from the pre-treatment to the post-treatment biopsy will be tested using the Wilcoxon sign test to determine if the change is less than zero, suggesting a decrease. To evaluate the drug's effects on circulating concentrations of angiogenic factors and cytokines, HIV and KSHV loads, and T-lymphocyte subsets, changes in these levels from pre-treatment to indicated sampling times will be tested by repeated-measures ANOVA, single and multivariate analysis.

For each subject, study drug administration will be described in terms of the actual doses administered and the proportion of drug actually delivered relative to the amount that should have been delivered. The total number of cycles administered; the median (range) of cycles administered; dose modifications, dose delays, and dose omissions; and reasons for deviations from planned therapy will be described by starting dose level. The type and timing of use of concomitant drugs will also be described.

AEs and laboratory abnormalities will be summarized by type and severity grade. First-cycle DLTs, adverse events leading to death or to discontinuation from treatment, and serious adverse events will be considered with special attention.

Pharmacokinetic parameters will be calculated using the actual sample collection times. Pharmacokinetic variables will be calculated from the plasma concentration data using standard compartmental and noncompartmental methods, as appropriate for the data. Variables of interest may include  $T_{max}$ ,  $C_{max}$ ,  $C_{24h}$ ,  $AUC_{0-24}$ , and  $t_{1/2}$ . Plasma concentrations and PK parameter results will be presented in tabular and graphic form by dose level and

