## APPENDIX I: SCHEDULE OF EVALUATIONS – *cont'd*

-  KS tumor assessments may be performed on Day 1 prior to receiving study treatment but may be performed no earlier than 14 days before initiating study treatment. Marker lesions and body areas must be photographed at baseline, then at each assessment when the response category changes.
-  To occur at Day 15 ( $\pm 2$  days) of Cycle 1, on Day 29 (Day 1 of Cycle 2) and every cycle (28 days) thereafter.
-  To occur at Day 29 (Day 1 of Cycle 2) and every three cycles thereafter.
-  To occur between Day 22 and 28 of Cycle 1. (Biopsy can occur as late as Day 29, but will need to be performed PRIOR to the first dose of study treatment in Cycle 2.)
-  To be collected immediately pre-dose; and at 1, 2, 3, 4, 5, 6 and 8 hours after the AM dose of study treatment on Day 1 of Cycle 1 and again at 1, 2, 3, 4, 5, 6 and 8 hours after the AM dose of study treatment on Day 28 of Cycle 1. **Note:** Day 28/Cycle 1 PK sampling may occur up to 3 days prior to Day 28 for scheduling purposes.
-  To be collected prior to the AM dose of study treatment on Day 15 ( $\pm 1$  day) of Cycle 1 and prior to the AM dose on Day 28 of Cycle 2 (or Day 1 of Cycle 3 if the subject's last dose of study treatment was the evening prior).
-  To be completed 30 days after discontinuation of study therapy.
-  To be collected pre-dose of study treatment on Day 1 of Cycle 1

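### A secondary objective covers CD4 and CD8, but only a CD4 count is scheduled, so the CD8 part has no required data source

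*Combined protocol and SAP*

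**What the plan says.** Section 2.2.4 sets the secondary objective "To describe the effects of PTC299 on T-lymphocyte subsets (CD4 and CD8", and the Schema carries the same objective. Section 11.2 gives the analysis. It lists circulating factors, viral loads "and T-lymphocyte subsets, changes in these levels from pre-treatment to indicated sampling times will be tested by repeated-measures ANOVA". It refers to subsets in the plural but does not name CD8.

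The assessments are set out as follows:

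- **Baseline (4.1.6):** the laboratory list includes a CD4 count.
- **On treatment (4.2.1.10):** "CD4 count on Day 29 (Day 1 of cycle 2) and every three cycles (12 weeks) thereafter".
- **Discontinuation (4.3.3):** "CD4 count and HIV plasma RNA viral load, and KSHV viral load".
- **30-day follow-up (4.4):** the list ends with "Karnofsky performance status (Appendix II), toxicity evaluation and cytokine assay" and contains no lymphocyte subset.
- **Appendix I:** one row for the CD4 count, timed by footnote 8, "To occur at Day 29 (Day 1 of Cycle 2) and every three cycles thereafter". There is no row for CD8 or for a subset panel.

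On enrolment, Section 11.1 records that "9 subjects have been enrolled into Stage 1, 8 subjects have been enrolled into Stage 2, and up to 21 subjects" are to enter Stage 3.

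**The concern.** The objective names two cell types and the schedule measures one. A site that follows the protocol exactly meets every requirement without obtaining a CD8 value. The planned analysis is of change from pre-treatment, so it needs a baseline value and at least one later value in the same subject. A baseline that was not measured cannot be recovered once dosing has begun. At stake is one component of one of six secondary objectives: the protocol commits to describing an effect for which it asks nobody to collect data.

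**Working it through.** No sample size, power or error-rate figure is involved. The check sets the objective against each list of assessments and then counts subjects.

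**Step 1. Scheduled measurements.**

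| Time | Source | CD4 | CD8 |
|---|---|---|---|
| Baseline | 4.1.6, Appendix I | yes | no |
| Day 29 | 4.2.1.10, Appendix I | yes | no |
| Every three cycles after Day 29 | 4.2.1.10, Appendix I footnote 8 | yes | no |
| Discontinuation | 4.3.3, Appendix I | yes | no |
| 30 days after treatment | 4.4, Appendix I | no | no |

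Scheduled CD8 measurements: zero at every time point. CD8 appears only in the two copies of the objective.

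**Step 2. Could another sample supply CD8?**

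- The blood count with differential does not separate T-cell subsets.
- CD8 is not among the named immunohistochemistry markers (4.2.2.1, Appendix XIII), the cytokines (4.2.4) or the RNA targets (Appendix V). The plan leaves room for other markers in these assays, but none is a blood T-cell count.
- The mononuclear cells for KSHV load go to DNA extraction and PCR (Appendix VI).
- The specimen-bank donation is optional and taken only at baseline or Day 1, so it cannot show change.

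None of these fills the gap.

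**Step 3. What an amendment could still recover.** The inputs are from Section 11.1.

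- Already enrolled: 9 + 8 = 17.
- Still to come: up to 21.
- Maximum evaluable: 17 + 21 = 38, which reproduces the protocol's figure.
- Prospective baseline CD8 possible in at most 21/38 = 55%.
- Baseline already past in 17/38 = 45%.

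**Step 4. Added laboratory work.** After Day 1 of cycle 2, every three cycles gives cycles 5, 8 and 11 within the 12-cycle limit. A subject treated for the full period would have 1 baseline + 4 on-treatment + 1 discontinuation = 6 CD8 results, all at draws already planned for CD4.

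**The case against.** The strongest reply is that laboratories may report CD8 alongside CD4, and that the case report forms may have a field for it. The forms and their instructions are supplied separately (Sections 9.0 and 10.1), so this cannot be excluded. It limits the claim: the documents show that CD8 is unscheduled, not that every CD8 value is missing or that nothing can be salvaged at analysis. It does not remove the gap, because the protocol neither requires CD8 nor asks for it to be recorded. Any values would depend on local practice. Elsewhere the protocol spells out the components it wants, such as direct and indirect bilirubin.

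A reader might infer three further things that the documents do not support:

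- **That objective 2.2.4 cannot be answered at all.** CD4 is measured at baseline, on treatment and at discontinuation, so that part stands.
- **That Section 11.2 explicitly promises a CD8 analysis.** It speaks only of T-lymphocyte subsets. Reading CD8 into that phrase from objective 2.2.4 is reasonable, but it is an inference.
- **That CD4 changes become uninterpretable without CD8.** No CD4/CD8 ratio or joint reading is planned, and the staging criteria in Appendix III use CD4 alone.

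It is also fair to say that the objective is secondary and descriptive. CD8 enters no eligibility criterion, dose-limiting toxicity definition, response definition, escalation or stopping rule, or sample size calculation. That bears on how much the gap matters, not on whether it exists.

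**Conclusion.** The point holds as an internal inconsistency between an objective and the schedule meant to serve it. No CD8 measurement is scheduled at any visit, so the CD8 part of objective 2.2.4 has no required data source, while the CD4 part remains answerable. If CD8 is added now, prospective baselines are available for at most 21 of 38 evaluable subjects.

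That ceiling assumes that Stage 3 enrols its full 21 and that none of them starts before the change takes effect. It treats the 17 already enrolled as having no CD8 baseline unless a site laboratory happened to report one. The correction is worth making because it is cheap and because each enrolment under the present wording lowers what can be recovered. Nothing in the primary objectives, the safety rules or the sample size depends on it.

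**What to change.** Choose one of two routes.

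1. **Measure CD8.** Replace the CD4 count with CD4 and CD8 counts in Sections 4.1.6, 4.2.1.10 and 4.3.3 and in Appendix I, at the existing visits and draws. State that prospective baseline CD8 will exist only for the Stage 3 subjects (up to 21), and that CD8 for the 17 already enrolled will be used only where the site laboratory had already reported it. The cost is one added laboratory result per existing CD4 draw, with no new visit.

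2. **Narrow the objective.** Delete CD8 from objective 2.2.4 and from the Schema, and change T-lymphocyte subsets to CD4 count in Section 11.2 so that the analysis matches. This costs three wording edits and leaves a narrower secondary objective.

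The choice is the sponsor's. What matters is that the objective, schedule and analysis agree.

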### **3.0 PATIENT SELECTION**

#### **3.1 Inclusion Criteria**

Subjects must meet all of the following conditions to be eligible for enrollment into the study:

- 3.1.1 Biopsy-proven KS involving the skin, with or without lymph node, oral cavity, gastrointestinal (GI) tract and/or lung involvement. GI and pulmonary involvement must be asymptomatic or minimally symptomatic and not require systemic cytotoxic chemotherapy. At least five measurable, previously non-radiated, cutaneous lesions must be present, which can be used as indicator lesions. Additionally, patients will need a sufficient number of non-indicator cutaneous lesions measuring  $\geq 4 \times 4$  mm to obtain a total of four (4) 3-mm punch biopsies, two at baseline and two during the course of treatment.
- 3.1.2 Serologic documentation of HIV infection at any time prior to study entry, as evidenced by positive ELISA, positive Western Blot, or other federally approved licensed HIV test, or a detectable blood level of HIV RNA.
- 3.1.3 Karnofsky performance status  $\geq 60$ .
- 3.1.4 The following laboratory parameters within 21 days prior to enrollment:
  - 3.1.4.1 Hemoglobin  $\geq 8$  g/dL.
  - 3.1.4.2 Absolute neutrophil count  $\geq 1,000$  cells/mm^3.
  - 3.1.4.3 Platelet count  $\geq 75,000$ /mm^3.
  - 3.1.4.4 Creatinine  $\leq 2.0$  mg/dL.
  - 3.1.4.5 Bilirubin values:
    - For patients who are not receiving indinavir or atazanavir, total serum bilirubin should be Grade 0 ( $\leq$  upper limit of normal [ULN]).
    - For patients who are receiving indinavir or atazanavir, there is no specific limit on total serum bilirubin, but direct serum bilirubin should be  $\leq 30\%$  of the total bilirubin.
  - 3.1.4.6 AST (SGOT) and ALT (SGPT)  $\leq$  Grade 1 (2.5 x ULN).
  - 3.1.4.7 INR and aPTT  $\leq$ ULN.
  - 3.1.4.8  $< 2+$  proteinuria.
- 3.1.5 Life expectancy  $\geq 3$  months.

- 3.1.6 Age  $\geq$  18 years.
- 3.1.7 Ability and willingness to give written informed consent.
- 3.1.8 Women of child-bearing potential must have a negative pregnancy test within 72 hours before initiation of study drug dosing. Post menopausal women must be amenorrheic for at least 12 months to be considered of non-childbearing potential.
- 3.1.9 Male and female patients of reproductive potential must agree to employ an effective barrier method of birth control throughout the study and for up to 3 months following discontinuation of study drug. (Note: A woman of childbearing potential is one who is biologically capable of becoming pregnant. This includes women who are using contraceptives or whose sexual partners are either sterile or using contraceptives.)
- 3.1.10 Patients must, in the opinion of the investigator, be capable of complying with the protocol.
- 3.1.11 Antiretroviral therapy for HIV infection is not required, but is recommended. Patients receiving antiretroviral therapy must be on a stable regimen for at least 12 weeks prior to study entry. Patients may receive any FDA approved antiretroviral therapy or agents available through a treatment IND. For patients receiving antiretroviral therapy, there should be no evidence for improvement in KS in the 3 months prior to study entry, unless there is evidence for progression of KS in the 4 weeks immediately prior to study entry.

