### Other Concomitant Medications

To the extent possible, administration of any prescription or over-the-counter drug products other than study medication should be minimized during the study period. It is expected, however, that subjects will be receiving antiretroviral therapy for their HIV infection, and may be receiving other drugs to prevent OIs; these are specifically allowed, as discussed in Section 5.4.1. Subjects should be discouraged from use of street drugs, health foods, herbal remedies, self-prescribed drugs, tobacco products, or excessive alcohol at any time during clinical studies of PTC299.

If considered necessary for the subject's well being, drugs for concomitant medical conditions or for symptom management may be given at the discretion of the investigator. The decision to authorize the use of any drug other than study medication should take into account subject safety, the medical need, the potential for drug interactions, the possibility for masking symptoms of a more significant underlying event, and whether use of the drug will compromise the outcome or integrity of the study.

Because it is possible that PTC299 may slow the clearance of drugs that are primarily metabolized by CYP2D6, investigators should pay specific attention to use of drugs that are known substrates of this enzyme, particularly when such drugs may have a low therapeutic index. Concomitantly administered substrates for CYP2D6 that may require special attention include certain chemotherapeutic drugs (anthracyclines and vinca alkaloids) most antidepressants (tricyclic antidepressants, selective serotonin reuptake inhibitors, and others), many antipsychotics, many beta-adrenergic receptor blockers, and certain anti-arrhythmics. In addition, several antiretroviral agents, including ritonavir, lopinavir/ritonavir, and delavirdine, rely to some extent on CYP2D6 for their clearance.

Subjects should be instructed about the importance of the need to inform the clinic staff of the use of any drugs or remedies (whether prescribed, over-the-counter, or illicit) before and during the course of the study. Any concomitant drugs taken by a subject during the course of the study and the reason for use will be recorded on the CRFs.

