#### 5.4.1 Permitted Medications

- Antiretroviral therapy for HIV infection
- Treatment, maintenance or chemoprophylaxis with approved agents for opportunistic infections as clinically indicated
- Topical and/or oral antifungal agents
- Antibiotics as clinically indicated
- Erythropoietin is permitted at the discretion of the Investigator
- Granulocyte colony stimulating factors as clinically indicated for > grade 3 neutropenia at the discretion of the Investigator.
- Regularly prescribed medications such as antipyretics, analgesics, allergy medications, antidepressants, sleep medications, oral contraceptives, megestrol acetate, testosterone or any other medications are permitted except for prohibited medications (see Section 5.4.2).

- Alternative therapies such as vitamins not exceeding the recommended daily allowance, acupuncture and visualization techniques will be permitted. Subjects should report the use of these therapies and they will be recorded.
- Use of aspirin or nonsteroidal anti-inflammatory drugs (NSAIDs) at doses not to exceed the maximum recommended dose is permitted.

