#### 5.4.2 Prohibited Medications

- Investigational drugs with the exception of antiretroviral agents that are being obtained through an expanded access protocol.
- Warfarin at any dose.
- Heparins, including low molecular weight heparins.
- Antiplatelet agents (e.g., clopidogrel bisulfate)
- Systemic cytotoxic chemotherapy or any other treatment specifically prescribed to treat KS (e.g., radiation, etc.).
- Routine use of systemic corticosteroid therapy other than replacement doses is not permitted.

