### APPENDIX I: SCHEDULE OF EVALUATIONS

	Eligibility	Screening/ Baseline	Day 1/ (Cycle 1)	Day 15 (Cycle 1)	Day 28 (Cycle 1)	Day 29 (Day 1 of Cycle 2)	Day 57 (Day 1 of Cycle 3)	Day 85 (Day 1 of Cycle 4)	Day 113 (Day 1 of Cycle 5)	Every 28 Days Thereafter	Treatment Discont.	Post- Treatment/ Early Discont. of Therapy
Informed Consent	X											
HIV Documentation	X 											
KS Biopsy (Diagnostic)	X 											
KS Biopsy (non-indicator KS lesion; IHC)		X			X 							
KS Biopsy (non-indicator KS lesion; viral gene expression & cellular gene transcription)		X			X 							
Skin Biopsy (morphologically normal skin)		X										
Complete Medical History		X 										
Complete Review of Signs and Symptoms		X 		X 		X 	X 	X 	X 	X 		
Complete Physical Exam (vital signs [temperature, pulse, BP, respiratory rate] height, weight)		X 		X 		X 	X 	X 	X 	X 	X	X 
KS Tumor Assessment	X 					X	X	X	X	X	X	X 
Karnofsky Performance Status	X 			X 		X 	X 	X 	X 	X 	X	X 
Concomitant Medication Review		X 		X 		X 	X 	X 	X 	X 		
Review of current and prior anti-HIV therapy, prior immune based therapy, and prior anti-tumor therapy		X 		X 		X 	X 	X 	X 	X 		
KS Staging		X										
Toxicity Evaluation				X 		X 	X 	X 	X 	X 	X	X 
CBC with Differential and Platelets		X 		X 		X 	X 	X 	X 	X 	X	
INR and aPTT	X 	X 		X 		X 	X 	X 	X 	X 		

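### Responses that follow an on-study start or change of antiretroviral therapy count in full in the single-arm test against 10%, so the response rate can be biased upward by an unknown amount

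*Combined protocol and SAP*

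**What the plan says.** **At entry.** Section 3.1.11 states that "Antiretroviral therapy for HIV infection is not required, but is recommended", so untreated patients can enrol. For those already treated it adds two conditions: "Patients receiving antiretroviral therapy must be on a stable regimen for at least 12 weeks prior to study entry", and "For patients receiving antiretroviral therapy, there should be no evidence for improvement in KS in the 3 months prior to study entry". The second is waived if KS has progressed in the last 4 weeks before entry.

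**On study.** Section 5.4 (Other Concomitant Medications) says "It is expected, however, that subjects will be receiving antiretroviral therapy for their HIV infection" and that this is allowed. Section 5.4.1 lists "Antiretroviral therapy for HIV infection" as permitted, with no stability condition. Section 5.4.2 prohibits cytotoxic chemotherapy and "any other treatment specifically prescribed to treat KS"; ART prescribed for HIV is not caught by that wording. Section 7.0 does not make an ART start or switch a reason to stop treatment.

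**Endpoint and analysis.** Section 8.1 defines CR and PR by lesions, edema and visceral disease only. Section 11.1 tests the CR + PR rate against 10% in a single arm. It stops at 1 or fewer responders among 11, otherwise adds 18-21 subjects, and rejects at 6 or more responders. It also gives a separate rule of 4 or more among 12 at the top dose. Section 11.2 estimates the response rate as a binomial proportion with a 95% confidence interval. No ART rule appears in any of these sections.

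**Data.** Appendix I schedules "Review of current and prior anti-HIV therapy, prior immune based therapy, and prior anti-tumor therapy" at baseline, Day 15 and every cycle. Section 11.2 promises a description of the type and timing of concomitant drugs.

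**The concern.** The entry condition that "there should be no evidence for improvement in KS in the 3 months prior to study entry" makes sense only if ART can itself improve KS. So the protocol, on its own terms, treats ART as a possible cause of the primary efficacy outcome. The protection it builds has two gaps: it does not cover patients who enter untreated and start ART later, and it does not cover regimen changes after entry.

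Estimating the response rate is a primary objective (2.1.3), and the test against 10% decides whether further study is warranted. With no control arm, a response caused by an ART start or switch cannot be separated from a response to PTC299 unless the analysis does so by rule. Any such response raises the estimate and moves the count toward the rejection threshold.

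**Working it through.** **Inputs from Section 11.1:** null rate 10%; continue if 2 or more of 11 respond; 18-21 further subjects, so n = 29 to 32 in total; reject at 6 or more responders; separate rule of 4 or more of 12.

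**Inputs not in the documents (assumptions):** f, the share of subjects who start or change ART on study; r, the share of those who respond to ART alone.

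**Step 1: reproduce the plan's figures (exact binomial).**
- P(1 or fewer of 11) at 10% = 0.697; the plan states 0.697.
- The same at 35% = 0.061; the plan states 0.059, a negligible difference.
- P(4 or more of 12) at 10% = 0.026; the plan states below 5%.

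**Step 2: two-stage rejection probability with no ART effect.**
P(reject) = sum over x1 = 2 to 11 of P(X1 = x1 of 11) × P(X2 ≥ 6 − x1 of n − 11).
At 10% this is 0.051 for n = 29 and 0.070 for n = 32. The excess over the nominal 0.05 comes from the final sample size and has nothing to do with ART.

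**Step 3: ART effect added to a rate of exactly 10%.**
A subject who would not otherwise respond (90%) responds through ART with probability f × r, so p = 0.10 + 0.90 × f × r.

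| f | r | p | ≥2/11 then ≥6, n = 29 | n = 32 | ≥4/12 |
|---|---|---|---|---|---|
| 0 | – | 0.100 | 0.051 | 0.070 | 0.026 |
| 10% | 30% | 0.10 + 0.027 = 0.127 | 0.125 | 0.162 | 0.056 |
| 20% | 30% | 0.10 + 0.054 = 0.154 | 0.234 | 0.288 | 0.100 |
| 20% | 50% | 0.10 + 0.090 = 0.190 | 0.408 | 0.473 | 0.180 |

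**Step 4: ART as the only source of response.** Now p = f × r.

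| f | r | p | n = 29 | n = 32 | ≥4/12 |
|---|---|---|---|---|---|
| 10% | 30% | 0.03 | 0.0001 | 0.0002 | 0.0003 |
| 20% | 30% | 0.06 | 0.005 | 0.008 | 0.004 |
| 20% | 50% | 0.10 | 0.051 | 0.070 | 0.026 |

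None of these exceeds the error rate that the design already has at 10%. To exceed it, f × r must itself be above 10%. For example, f = 30% and r = 50% give 15%, with rejection 0.216-0.268 for the two-stage rule and 0.092 for 4 of 12.

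**Step 5: sensitivity to one subject.** If one of the 12 top-dose subjects responds because of ART, the 4-of-12 rule needs 3 or more of the other 11. At 10% that has probability 0.090, against 0.026 without that subject.

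**The case against.** The strongest reply is that the inflation in Step 3 depends on a non-ART rate sitting exactly at the null. Section 11.1 does not say how the 10% was derived, and it may already allow for background regression. A reader might infer that ART alone could carry an inert drug past the 10% test. Step 4 does not support that for the scenarios considered; it would take an ART-driven response rate above 10% across all subjects. This objection stands and limits the claim.

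Three further points have weight:
- **f and r have no source.** Section 5.4 expects subjects to be on ART, and 3.1.11 requires those already treated to be stable, so starts and switches may be few.
- **The window is shorter than 48 weeks.** The Schema and Section 7.0 remove subjects without an objective response after six cycles, so a first response must normally appear within about 24 weeks on treatment.
- **The word recommended stands in an inclusion criterion.** A reader might take it as advice to start ART after enrolment, but the text does not say so.

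It can also be said that 11.2 already describes concomitant drug timing and that, with about six responders, each case could be inspected. This stands only in part. Description does not settle how a response is counted, and a case-by-case judgment made with the responses known is what a pre-specified rule avoids.

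**Conclusion.** The gap is real and should be closed. The entry rules show that the protocol regards ART-related KS improvement as a threat to the endpoint, yet nothing after entry restricts or accounts for it, and the possible bias in the response rate is upward.

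The size cannot be established from the documents. With a non-ART rate of exactly 10%, the assumed scenarios put rejection at 0.125 to 0.473 under the two-stage rule (base 0.051-0.070) and at 0.056 to 0.180 under the 4-of-12 rule (base 0.026). With ART as the only source of response, the same scenarios give at most 0.070.

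The documents therefore do not support the stronger conclusion that a false-positive result is likely. What they support is that a positive result could depend on responses whose cause the planned analysis cannot distinguish.

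**What to change.** Add to Section 11.2, before responders' ART histories are examined:

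- A pre-specified analysis in which a response first documented after a subject starts ART, or switches regimen for any reason other than a like-for-like tolerability substitution, counts as a non-response. The exception keeps trivial swaps from cancelling genuine responses.
- That rate, with its 95% confidence interval and its count against the 6-responder and 4-of-12 thresholds, reported beside the all-response result.
- A statement that a rejection that depends on responses after an ART start or switch is not attributed to PTC299 alone.

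If the rate without ART changes is no more than 10%, and exempt substitutions do not themselves produce responses, the rate counted in this analysis is also at most 10%. Its rejection probability is then at most 0.051-0.070 for the two-stage rule and 0.026 for 4 of 12, the design's own figures.

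**Cost:** a short paragraph and one table. Anti-HIV therapy is already reviewed at Day 15 and every cycle, so no new visit or assessment is needed; the reason for a switch must be recorded. The downside is that a true drug response after an ART change is not credited in this analysis, which is why the all-response count stays beside it. No change to ART use is proposed.
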